Patients who are lost to follow-up or withdrawn prior to the 2 month follow-up visit due to an RA or RV lead related complication will be analyzed as having experienced a complication at the date the complication occurred. Patients who withdraw for reasons unrelated to an RA or RV lead related complication will be censored at the date of withdrawal.

Analysis

The desired outcome is to reject both null hypotheses for the RA and RV endpoints. The RA and RV hypothesis will be tested separately. The null hypothesis for the RA or RV endpoints will be rejected at the 2.5% significance level if the 95% lower limit of a two-sided confidence interval for the freedom from RA or RV lead-related complications by 2 months is greater than 92%. The confidence

interval will be constructed using the log-log transformation of the event free estimate at 2 months.

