Patients who are lost to follow-up or withdrawn prior to the 12 month follow-up visit due to an RA or RV lead related complication will be analyzed as having experienced a complication at the date of the complication. Patients who withdraw for reasons unrelated to an RA or RV lead related complication will be censored at the date of withdrawal.

Analysis

The desired outcome is to reject both null hypotheses for the RA and RV endpoints. The RA and RV hypothesis will be tested separately. The null hypothesis for the RA or RV endpoints will be rejected at the 2.5% significance level if the 95% lower limit of a two-sided confidence interval for the freedom from RA or RV lead-related complications between 2 months and 12 months is greater than 95%. The confidence interval will be constructed using the log-log transformation of the event free estimate at 12 months.

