4.2.2 Primary MRI Safety Endpoint: Freedom from MRI Scan-Related complications

An MRI Scan-Related complication is a complication caused by the interaction between the investigational pacing system and the MRI system that occurs during the MRI scan, including the time the patient is within the 5 Gauss line of the MRI system, up through the patient's 1 month post MRI visit. In addition, complications occurring due to the patient's MRI programming will be considered MRI scan related by the Clinical Events Committee (CEC).

The hypothesis is formally expressed as:

H_0 : Proportion of patients who are free from MRI scan-related complications between the MRI scan and one month post MRI visit $\leq 90\%$

H_a : Proportion of patients who are free from MRI-scan related complications between the MRI scan and one month post MRI visit $> 90\%$

The comparison criterion of 90% used for this objective denotes the minimum level for adequate safety following the MRI scan. Complications that can be attributed to the MRI scan are expected to occur within one month of the scan.¹⁹ Therefore, assessing this objective one month post-MRI scan will capture all MRI scan-related complications following the MRI scan procedure.

Sample Size

The expected proportion of patients free from complications under the null hypothesis is 0.90, and the Type 1 error rate is set at $\alpha = 0.025$ for the one-sided test. Assuming the portion of patients free from complications of 0.97, a sample size of 133 MRI patients provides a power level of 90% for this endpoint.

In another manufacturer's study involving an MRI conditional pacemaker, the complication free rate as observed to be 100%.¹⁹ Therefore, an assumption of 97% complications-free rate is assumed in the sample size calculation.

The objective will be evaluated using a one-sided z-test with variance of the test statistic based on the hypothesized value of 0.90 for the binomial proportion. The desired outcome is to reject the null hypothesis.

Patient Group

All patients implanted with the Accent MRI system who undergo an MRI scan and have completed their 1 month post MRI visit, or have an MRI-related complication before the end of the 1 month post MRI visit date will be included in the analysis of this endpoint.

Analysis

The analysis will be conducted on the per-protocol (PP) population. The per-protocol population includes patients who meet the following criteria:

- Successfully implanted with the Accent MRI system

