- Have MRI visit data
- Meet the MRI Conditions of Use
- Received an MRI scan
- Have 1-month post MRI visit data

All individual primary safety endpoints must be successful (reject the null hypothesis at the $\alpha = 2.5\%$ level) for the safety endpoint to be successful.

A supporting analysis will also be performed using all patients who undergo an MRI scan. For this analysis, each missing data point will be replaced by a failure one at a time. Each time a new failure is added the analysis will be re-run. This continues until either all missing data has been replaced with a failure or the test becomes non-significant (i.e. the interpretation of the results changes). The proportion of missing data that would need to be a failure in order to change the analysis results will be reported and discussed.

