4.2.4.1 Freedom from system-related complications

The hypothesis is formally expressed as:

H_0 : Freedom from system related complications through the 12 month visit $\leq 80\%$

H_a : Freedom from system related complications through the 12 month visit $> 80\%$

The desired outcome is to reject the null hypotheses. The null hypothesis will be rejected at the 5% significance level if the 95% lower confidence limit for the freedom from system related complications at 12 months is greater than 85%.

Simulation was used to calculate the sample size requirements for testing the Kaplan-Meier estimated survival probability for the freedom-from-complication endpoint. The expected proportion of patients free from system related complications at 12 months is 0.975 (95% CI: 0.924, 0.992) using data from the VICTORY pulse generator IDE study (G050191). For a study size of 800 patients and a Type 1 error rate for the hypothesis test of $\alpha = 0.05$ for a one-sided test, the power is greater than 98%.

Patient Group

All patients that have had an attempted implant or a successful implant of an Accent MRI system will be included in this endpoint.

Patients who are lost to follow-up or withdrawn prior to the 12 month follow-up visit due to a system related complication will be analyzed as having experienced a complication at the date of withdrawal. Patients who withdraw for reasons unrelated to a system related complication will be censored at the date of withdrawal.

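### Section 4.2.2 gives two conflicting inclusion rules for the primary MRI safety test; read literally, the per-protocol list can drop only known failures

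*Combined protocol and SAP*

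**What the plan says.** Section 4.2.2 (Primary MRI Safety Endpoint) tests whether more than 90% of scanned patients are free from MRI scan-related complications up to the 1-month post MRI visit. It states who is analysed in two places.

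- **Patient Group.** Scanned patients who completed the 1-month visit, "or have an MRI-related complication before the end of the 1 month post MRI visit date will be included".
- **Analysis.** "The analysis will be conducted on the per-protocol (PP) population". The list of criteria that follows ends with "Have 1-month post MRI visit data".

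A secondary check follows: "A supporting analysis will also be performed using all patients who undergo an MRI scan". In it, "each missing data point will be replaced by a failure one at a time" until the missing points run out or significance is lost.

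Other endpoints say what happens to a patient who leaves because of a complication. For the acute lead endpoints (4.2.1.1 and 4.2.1.2) the patient "will be analyzed as having experienced a complication at the date the complication occurred". For the chronic lead endpoints (4.2.1.3 and 4.2.1.4) the patient "will be analyzed as having experienced a complication at the date of the complication". For the secondary system endpoint (4.2.4.1) the patient "will be analyzed as having experienced a complication at the date of withdrawal".

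**The concern.** The two statements in 4.2.2 agree for every scanned patient with 1-month data who meets the other criteria. They also agree for a scanned patient with neither a visit nor a complication, who is left out under both. They disagree about a patient with a known complication and no 1-month data. The Patient Group sentence counts that patient as a failure. The per-protocol list, taken at its word, removes the patient from numerator and denominator.

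The disagreement therefore concerns failures only, and any bias from the literal list runs in the device's favour. The endpoint is pass or fail, every primary safety and efficacy endpoint must succeed for overall success (end of 4.2.3), and the secondary endpoints are tested only after that (4.2.4). Whether a known failure counts in a primary safety test should be settled before data are seen.

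**Working it through.** **Inputs, all from 4.2.2 unless stated.** Null proportion 0.90; design proportion 0.97; one-sided alpha 0.025; z-test with the variance taken at 0.90; stated size 133 for 90% power. Maximum size of the MRI phase 363 (4.1).

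**1. The plan's own sample size.**

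n = [(1.960 × √(0.90 × 0.10) + 1.282 × √(0.97 × 0.03)) / (0.97 − 0.90)]² = [(0.5880 + 0.2186) / 0.07]² = 132.8, rounded up to 133. The stated figure reproduces.

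**2. Pass limit.** With f failures among n patients, z = ((n − f)/n − 0.90) / √(0.09/n), and the test passes if z > 1.960.

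| Failures / patients | z | Result |
|---|---|---|
| 6 / 133 | 2.110 | pass |
| 7 / 133 | 1.821 | fail |
| 25 / 363 | 1.977 | pass |
| 26 / 363 | 1.802 | fail |

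The limit is 6 failures at n = 133 and 25 at n = 363.

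**3. Dropping known failures, as the literal list would.**

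| Patient Group rule | Dropped | Literal list | z under the list | Result |
|---|---|---|---|---|
| 7 / 133, fail | 1 | 6 / 132 | 2.089 | pass |
| 8 / 133, fail | 1 | 7 / 132 | 1.799 | fail |
| 8 / 133, fail | 2 | 6 / 131 | 2.068 | pass |
| 26 / 363, fail | 1 | 25 / 362 | 1.962 | pass |
| 27 / 363, fail | 2 | 25 / 361 | 1.947 | fail |
| 27 / 363, fail | 3 | 24 / 360 | 2.108 | pass |

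One lost failure matters only exactly at the limit. Further out, more must be lost.

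**4. How often this could happen.** The documents do not say what share q of complications would lack 1-month data, so q is an assumption, shown over a range. Let F ~ Binomial(n, 0.03) be the complications at the design rate and D ~ Binomial(F, q) those without the visit. The table gives the probability that F of n fails while F − D of n − D passes. The row for 165 is included because the atrial sensing endpoint (4.2.3.3) needs that many analysable patients.

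| n | q = 1% | 5% | 10% | 20% |
|---|---|---|---|---|
| 133 | 0.4% | 1.9% | 3.7% | 6.4% |
| 165 | 0.3% | 1.4% | 2.6% | 4.3% |
| 363 | ≤ 0.005% | ≤ 0.005% | ≤ 0.005% | ≤ 0.005% |

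**5. If the true complication-free rate were exactly 90%.** The probability of a pass is the type I error.

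| n | q = 0 | 5% | 10% | 20% |
|---|---|---|---|---|
| 133 | 0.017 | 0.026 | 0.040 | 0.085 |
| 363 | 0.025 | 0.040 | 0.066 | 0.190 |

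This is the unfavourable case, far from the design assumption, and it rests on the same unsupported q.

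**The case against.** **The text is ambiguous and does not order a failure to be dropped.** A reader might infer that the per-protocol list overrides the Patient Group sentence. No text says so. That sentence is specific to this endpoint and this case, whereas the five list items also open the efficacy lists in 4.2.3. Reading the sentence as an exception to the list is at least as natural, because the literal list leaves its second clause with no effect. This stands: the defect is an unresolved conflict.

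**Explant is a weak route.** A reader might infer that a scanned patient whose system is explanted without replacement always leaves before the visit, since 4.4.4 provides for withdrawal and its form list has no Follow Up Form. But 4.4.4 follows the patient for 30 days. If these run from the explant, the patient is still under follow-up when the 1-month window (±7 days, Table 4) opens. Section 4.4.6.7 asks for the visit in all MRI-phase patients, and the explant reason listed in section 9.0 is limited to patients not yet scanned. This largely stands. The route remains only if the 30-day contact is not accepted as the 1-month visit, which the plan does not settle. Death or withdrawal after a complication is a clearer route but narrow, because a complication must require invasive intervention (4.2.7).

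**Other safeguards exist.** The events committee adjudicates every adverse event (6.0), the safety board reviews safety data (6.1), and the all-scanned analysis would include the patient. So the event would not be hidden. None of these decides the primary test, however, and the supporting analysis does not say that a known complication without a visit is a failure from the start and not one of the missing points.

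**Complications from MRI programming.** A reader might infer a further gap because MRI mode is activated before the scan. The endpoint definition in 4.2.2 already counts programming-related complications, so no change to the event window is needed.

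**Conclusion.** The contradiction is real and in current text. Taken literally, the per-protocol list can remove only known failures, so its error can only help the device. The size is minor. The result changes only when the failures lost cover the excess over the pass limit: one at 7/133 or 26/363, more beyond that. At the design rate of 3% the chance of this is a few per cent at most at n = 133 and negligible at n = 363. These chances rest on an assumed share of complications without 1-month data, for which the documents give no figure. The documents do not support the stronger statement that the plan will exclude known failures, because they do not say which rule prevails. The sample size of 133 is correct and unaffected.

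**What to change.** In 4.2.2, change the last per-protocol item to: *1-month post MRI visit data are available, or the patient had a CEC-adjudicated MRI scan-related complication before the end of the 1-month post MRI visit window, in which case the patient is included and counted as a failure.*

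Add to the supporting analysis: *Known complications are failures from the start; one-at-a-time replacement applies only to patients whose status is unknown.*

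The cost is wording in one section. The Adverse Event Form is already in use at the MRI visit, at the 1-month visit and at explant (4.4.6.6, 4.4.6.7 and 4.4.4), and adjudication of all adverse events is already planned. The size of 133 and the efficacy populations stay as they are. Scanned patients with neither a visit nor a complication stay out of the primary count, as both rules already have it. The downside for the sponsor is a possibly slightly lower observed success rate. The edit does not touch the other per-protocol items: a scanned patient with a complication who did not meet the conditions of use would still be seen only in the supporting analysis.

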4.2.3 Primary MRI Efficacy Endpoints

4.2.3.1 Proportion of patients free of atrial capture threshold increase of > 0.5V at 0.5ms from before and to one month after the MRI scan

4.2.3.2 Proportion of patients free of ventricular capture threshold increase of > 0.5V at 0.5ms from before to one-month after the MRI scan

The hypothesis is formally expressed as:

H_0 : Proportion of patients with threshold increase of $\leq 0.5V$ at 0.5ms from before to one month post MRI visit $\leq 90\%$

H_a : Proportion of patients with a threshold increase of $\leq 0.5V$ at 0.5ms from before to one month post MRI visit $> 90\%$

The desired outcome is to reject the null hypothesis. The null hypothesis is rejected at 2.5% significance level if the lower bound of the two-sided 95% confidence bound on the proportion of patients with a threshold increase of $\leq 0.5V$ at 0.5ms from before to one month post MRI visit is greater than 90%.

Sample Size

A success (Post-MRI scan Threshold – Pre-MRI scan Threshold) is defined as a patient who experiences an increase in threshold less than or equal to 0.5 volts at the 1 month post-MRI visit compared to their pre-MRI testing (MRI visit). In this case post MRI capture Threshold \leq pre MRI capture Threshold + 0.5 volts.

The % of Success (Post-MRI scan Threshold – Pre-MRI scan Threshold) is defined as the number of patients with successes divided by the analyzable patients.

In another manufacturer's study involving an MRI conditional pacemaker, the proportion of patients with an increase in threshold less than or equal to 0.5 volts at the 1 month post-MRI visit compared to their pre-MRI testing was 100%.¹⁹ Therefore, an assumption of 98% of successes (Post MRI scan-Pre-MRI scan threshold) in the atrium and ventricle is assumed in the sample size calculation.

A sample size of 93 patients provides 90% power to demonstrate a success rate greater than 90% for the atrial and ventricular endpoints, respectively, at the 2.5% significance level.

Analysis

The analysis will be conducted on the per-protocol population. The per-protocol population includes patients who meet the following criteria:

- Successfully implanted with the Accent MRI system
- Have MRI visit data
- Meet the MRI Conditions of Use
- Received an MRI scan
- Have 1 month post MRI visit data
- Have a pacing threshold difference not exceeding 0.5 V at 0.5 ms between the two-month and MRI visit device pre-check, in cases where the MRI visit occurs approximately 9-12 weeks after the implant or system revision procedure since such short-term variability in pacing performance can be indicative of an abnormal lead/tissue interface that could confound analyses of MRI related effects.
- Have an atrial lead to be included in the '% success (change in atrial capture threshold)' endpoint analysis and/or a ventricular lead to be included in the '% success (change in ventricular capture threshold)' endpoint analysis
- Are not in AF at the time of atrial capture threshold measurements. Note: If atrial arrhythmias persist throughout the visit window for the MRI and/or 1 Month Post MRI visit, and no atrial capture threshold value can be obtained either at the MRI and/or 1 Month Post MRI visit, measured atrial capture threshold values from the next nearest timed visit may be substituted.

The proportion of patients not experiencing increases of 0.5V at 0.5ms for both atrial and ventricular capture thresholds will be calculated separately along with the associated 2.5% lower confidence bound. The lower bound for both of these proportions will be compared to the

OPC of 90%. The endpoints will be considered successful if the lower bound is greater than 90%.

Additional Analyses

A sensitivity analysis of the endpoint will be conducted using the ITT population, where both a worst and best case analysis will be performed. The worst case analysis will consist of treating all missing data as failures. The best case analysis will treat all missing data as successes.

4.2.3.3 Proportion of patients with atrial sensing amplitude decrease of $\leq 50\%$ and a sensing amplitude at 1-month post MRI visit of $\geq 1.5\text{mV}$

The hypothesis for the atrial sensing threshold is formally expressed as:

H₀: Proportion of patients with an atrial sensing amplitude decrease of $\leq 50\%$ and atrial sensing amplitude at 1-month post MRI visit of $>1.5\text{ mV} \leq 85\%$

H_a: Proportion of patients with an atrial sensing amplitude decrease of $\leq 50\%$ and atrial sensing amplitude at 1-month post MRI visit of $\geq 1.5\text{ mV} > 85\%$

The null hypothesis is rejected at 2.5% significance level if the lower bound of the two-sided 95% confidence interval on the proportion of patients with an atrial sensing amplitude decrease of $\leq 50\%$ and atrial sensing amplitude at 1-month post MRI visit of $\geq 1.5\text{mV}$ is greater than 85%.

4.2.3.4 Proportion of patients with ventricular sensing amplitude decrease of $\leq 50\%$ and a sensing amplitude at 1-month post MRI visit of $\geq 5\text{mV}$

The hypothesis for the ventricular sensing threshold is formally expressed as:

H₀: Proportion of patients with a 'ventricular sensing amplitude decrease of $\leq 50\%$ and ventricular sensing amplitude at 1-month post MRI visit of $>5\text{ mV}' \leq 87\%$

H_a: Proportion of patients with a 'ventricular sensing amplitude decrease of $\leq 50\%$ and atrial sensing amplitude at 1-month post MRI visit of $\geq 5\text{ mV}' >87\%$

The null hypothesis is rejected at 2.5% significance level if the lower bound of the two-sided 95% confidence interval on the proportion of patients with a ‘ventricular sensing amplitude decrease of $\leq 50\%$ and ventricular sensing amplitude at 1-month post MRI visit of $\geq 5\text{mV}$ ’ is greater than 87%.

Sample Size

A success is defined as a patient who experiences a decrease in sensing amplitude not exceeding 50%, and a sensing amplitude not less than 5 mV for ventricular measurements and not less than 1.5mV for atrial measurements at the 1 month post-MRI visit from the pre-MRI testing (at MRI visit).

The % of Success (Post-MRI scan Amplitude – Pre-MRI scan Amplitude) is defined as the number of patients with successes divided by the number of analyzable patients.

In another manufacturer’s study involving MRI conditional pacemaker, proportion of patients with ‘sensing amplitude decrease of $\leq 50\%$ and atrial sensing amplitude at 1-month post MRI visit of $\geq 1.5\text{mV}$ ’ was approximately 93%. In the same study, the proportion of patients with ‘sensing amplitude decrease of $\leq 50\%$ and ventricular sensing amplitude at 1-month post MRI visit of $\geq 5\text{mV}$ ’ was approximately 95%.¹⁹ Therefore, an assumption of 93% for successes in the atrium and 95% successes in the ventricle is assumed

A sample size of 165 patients provides 90% power for the atrial endpoint and 138 patients provides 90% power for the ventricular endpoint at the 2.5% significance level.

Analysis

The analysis will be conducted on the per-protocol population. The per-protocol population includes patients who meet the following criteria:

- Successfully implanted with the Accent MRI™ system
- Have MRI visit data
- Meet the MRI Conditions of Use
- Received an MRI scan (if in the MRI group)
- Have 1-month post MRI visit data
- Have a pacing threshold difference not exceeding 0.5V between the two-month and three month post-implant (MRI scan pre-check), in cases where the MRI visit takes place approximately 9-12 weeks after an implant or system revision procedure since such short-term variability in pacing

performance can be indicative of an abnormal lead/tissue interface that could confound analyses of MRI related effects.

- Have a pre-MRI/pre-waiting period sensing amplitude greater than or equal to 5.0 mV in the ventricle or greater than or equal to 1.5 mV in the atrium.
- Have an atrial lead to be included in the ‘% success (change in atrial sensing amplitude)’ endpoint analysis and/or a ventricular lead to be included in the ‘% success (change in ventricular sensing amplitude)’ endpoint analysis
- Are not in AF at the time of atrial sensing amplitude measurements
- Have an intrinsic heart rate ≥ 30 beats per minute at the time of ventricular and/or atrial capture threshold measurements

The proportion of patients not experiencing an atrial sensing amplitude decrease of $\leq 50\%$ and atrial sensing amplitude at 1-month post MRI visit of >1.5 mV will be calculated. The associated 2.5% lower confidence bound will also be derived. This lower bound will be compared to the OPC of 85% and the endpoint will be considered successful if the lower bound is greater than 85%.

The proportion of patients not experiencing a ventricular sensing amplitude decrease of $\leq 50\%$ and ventricular sensing amplitude at 1-month post MRI visit of > 5 mV will be calculated. The associated 2.5% lower confidence bound will also be derived. This lower bound will be compared to the OPC of 87% and the endpoint will be considered successful if the lower bound is greater than 87%.

All individual primary efficacy endpoints must be successful (reject the null hypothesis at the $\alpha = 2.5\%$ level) for the efficacy endpoint to be successful.

Additional Analyses

The same additional analyses described above in section 4.2.3.1 and 4.2.3.2 will be completed for this endpoint if required.

The overall success for the primary endpoints is achieved if all primary safety and primary efficacy endpoints are successful.

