4.0 Clinical Protocol

4.1 Study Design and Scope

This is a prospective, multi-center, clinical study designed to evaluate the safety and efficacy of the Accent MRI System in a patient population indicated for implant of a pacemaker within and outside of the MRI environment.

The study will be conducted at a minimum of 60 centers and a maximum of 80 centers worldwide. The minimum requirement for completing this study is 800 patients. A maximum of 120 (15% of the total) enrollments will be allowed per center. It is anticipated that at least 30% of enrollments will include patients implanted with the Tendril MRI lead in the right atrium.

Within the MRI environment, The Accent MRI system will be evaluated in conjunction with the MRI Activator. The MRI Activator performance will be evaluated qualitatively during this phase of the study. Up to 363 patients, including patients who were randomized to the MRI Control Group in previous versions of the investigational plan, will be enrolled in this phase of the study.

Enrollment in the MRI clinical study is expected to take approximately 12 months. The anticipated duration of this study is 32 to 34 months, depending on the rate of enrollment. All patients will be implanted with an Accent MRI pacemaker and a Tendril MRI lead. Devices implanted outside the United States will utilize different device model numbers.

The following study evaluations will occur after implant:

- Post implant follow up (pre-discharge)
- 2 month visit (post implant, in-office)
- 6 month visit (post implant, in-office)
- 12 months visit (post implant, in-office)
- Every 6 months post implant until study completion

MRI visits will consist of:

- MRI visit which includes:
 - Pre-MRI scan testing
 - MRI scan
 - post MRI testing
- 1 month post MRI visit

The schedule of follow up visits for the lead safety component of the study is based on the date of implant of the Accent MRI System. The follow up schedule for the MRI visit is based on the date of implant or revision of an MRI lead until the MRI visit; the MRI visit should take place no sooner than one week after the 2 month post implant or system revision procedure where the Tendril MRI lead was implanted, repositioned or replaced. The one month post MRI follow up visit is based on the MRI visit.

Figure 2: Lead Safety Phase Flow Diagram

[figure not shown]
[figure not shown]

Figure 3: MRI Phase Flow Diagram

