4.2.6 Additional Data

- Ability to identify radiopaque identification marker on the pacemaker and lead through X-ray review by a cardiologist and radiologist
- Adverse Events – system, lead, and implant procedure related events (not including the primary safety endpoint)
- Atrial and ventricular bipolar capture thresholds immediately after MRI scan
- Atrial and ventricular unipolar capture thresholds before and after the MRI scan
- Atrial and ventricular bipolar lead impedance through the 1 month post MRI visit
- Atrial and ventricular bipolar sensing thresholds immediately after MRI scan
- Cardiac medications
- Challenges and lessons learned in communication between the MRI/Radiology and Cardiology teams

- Demographics: gender, age, ethnicity, race, cardiac disease history, arrhythmia history, indication for pacemaker implant, history of smoking, etc.
- Inadequate equipment availability during MRI scan
- Incidence of aberrant or undesirable behavior of the device while in the MRI mode.
- Incidence of MRI related arrhythmias and asystole
- Lead handling characteristics
- Loss or lapses in patient monitoring during the MRI scan
- Mortality
- MRI Activator performance and usability
- MRI image qualitative analysis; St. Jude Medical will provide data on the image quality/presence of artifact for the first 20 MRI scans performed. Each participating site will be asked to submit the first five MRI scans performed (up to 5 scans maximum) until 20 total scans have been submitted.
- Number of non-study related MRI scans
- Preliminary study phase small cohort - St. Jude Medical will summarize the adverse event data on the first 44 patients who complete the one month post MRI scan (29 MRI, 15 Control). This summary will be provided to the FDA.

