4.4.6.2 Enrolling Patients into the MRI Phase of the Study

Consider all patients for participation in the MRI portion of the study regardless of gender. It is required that the MRI safety screening form be completed as part of the MRI screening for all patients who agree to participate in the MRI portion of the study to ensure there are no current contraindications for an MRI scan (See Appendix A). If a patient is contraindicated for the MRI scan based on the study exclusion criteria, the patient is NOT eligible for participation in the MRI portion of the study.

Obtain informed consent from the patient.

Important Note: MRI Control Patients enrolled under Revision J of the Protocol: This revision of the protocol, Revision K, allows patients previously enrolled into the MRI Phase under Revision J and who were randomized to the MRI Control Group, to now undergo the study MRI scans. To do so, obtain informed consent from the patient.

Patients enrolled and randomized under protocol Revision J to the MRI Control Group who have not completed an MRI Visit or a 1 Month Post MRI visit, AND who do not want to undergo the study MRI scans should be discontinued from the MRI Phase. To do so, complete and submit the MRI Discontinuation Form under the MRI Control visit in RDC.

Patients who have a Tendril MRI lead(s) implanted in or through the jugular are NOT eligible for participation in the MRI portion of the study.

Data Submission

Complete and submit the forms listed below to St. Jude Medical.

- MRI Enrollment Form

- MRI Discontinuation Form, if applicable

It is recommended that the following completed forms be maintained at the site:

- MRI Safety Screening Form
- MRI Hazard Checklist

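### The per-protocol list for the two primary sensing endpoints still requires a scan only of patients in the MRI group, so on a literal reading unscanned former Control patients can enter and dilute a scan effect on sensing.

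*Combined protocol and SAP*

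**What the plan says.** Three per-protocol lists govern the five primary MRI endpoints.

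- **MRI safety (4.2.2) and capture threshold (4.2.3.1, 4.2.3.2):** each lists "Received an MRI scan" with no condition.
- **Sensing amplitude (4.2.3.3, 4.2.3.4):** the criterion is "Received an MRI scan (if in the MRI group", with the closing bracket following. The baseline criterion in the same list reads "Have a pre-MRI/pre-waiting period sensing amplitude greater than or equal to 5.0 mV in the ventricle", with a matching atrial limit of 1.5 mV.

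The sensing list also asks for MRI visit data and 1-month post MRI visit data. Section 4.2 describes lead efficacy as change before and after the scan, and the success definition in 4.2.3.4 refers to post-scan and pre-scan amplitudes.

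On former Controls, Section 4.1 sets the MRI phase at "Up to 363 patients, including patients who were randomized to the MRI Control Group in previous versions of the investigational plan". Section 4.4.6.2 lets them consent to a scan, and discontinues from the MRI phase those "who have not completed an MRI Visit or a 1 Month Post MRI visit, AND who do not want to undergo the study MRI scans".

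**The concern.** The sensing endpoints are meant to show that a scan does not degrade sensing. A patient who was not scanned carries no information on that and pulls the pooled success rate towards the rate seen without a scan.

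The sensing list has two remnants of a control arm: the conditional scan criterion, and a baseline taken before a waiting period that the current MRI visit (4.4.6.6) does not contain. Section 4.4.6.2 itself speaks of Controls completing an MRI Visit and a 1 Month Post MRI visit, which are the visits named in the list. Its discontinuation rule covers only those who have not completed the visits and who decline the scan. Nothing in the documents removes a Control who completed both visits unscanned and did not come back.

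If such patients are counted, a loss of sensing in scanned patients could be partly hidden, and the four efficacy endpoints would rest on different kinds of patient: scanned only for capture, possibly mixed for sensing.

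**Working it through.** **Inputs from 4.2.3.3 and 4.2.3.4.** OPC 85% atrial, 87% ventricular. Expected success 93% and 95%. Lower limit of a two-sided 95% interval, so one-sided 2.5%. Sample sizes 165 and 138 for 90% power.

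**Input not in the documents.** The number of Controls who completed both visits unscanned and were never scanned. I vary it. The only Control count is in the adverse-event summary in 4.2.6: "patients who complete the one month post MRI scan (29 MRI, 15 Control", with the closing bracket following. I use 15 as one scenario, and one third (15/44 = 34%) as an upper assumption.

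**Step 1: the plan's sample sizes.** With the null variance under the null,
n = [1.960·√(p0(1−p0)) + 1.2816·√(p1(1−p1))]² / (p1−p0)².
- Atrial: [1.960·√0.1275 + 1.2816·√0.0651]² / 0.08² = 164.7, so 165.
- Ventricular: [1.960·√0.1131 + 1.2816·√0.0475]² / 0.08² = 137.6, so 138.

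Both reproduce.

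**Step 2: pass marks and error with scanned patients only.** With the exact (Clopper-Pearson) lower limit, the smallest passing counts are 150/165 (90.9%) and 128/138 (92.8%). The Wilson limit gives the same counts. Exact type I error is 1.7% and 2.4%; exact power is 88.3% and 91.4%.

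**Step 3: mixed set.** Successes = Binomial(scanned, OPC) + Binomial(unscanned, 93% or 95%). The false-pass probability is the chance that the sum reaches the pass mark.

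| Unscanned share | Atrial, n = 165 | Ventricular, n = 138 |
|---|---|---|
| none | 1.7% | 2.4% |
| 10% (16; 14) | 3.2% | 4.3% |
| 20% (33; 28) | 5.9% | 7.5% |
| one third (55; 46) | 12.1% | 14.3% |

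**Step 4: 15 unscanned patients.** Pass marks are 323/363 atrial and 329/363 ventricular; with 257 patients they are 230 and 235.

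| Set | Atrial | Ventricular |
|---|---|---|
| 348 scanned + 15 | 2.6% (1.7% if all 363 scanned) | 3.1% (2.0%) |
| 242 scanned + 15 | 3.6% (2.3% if all 257 scanned) | 2.9% (1.8% rounded up from 1.75%) |

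**Step 5: how a result could change at one third.**
- Atrial: 99/110 scanned (90.0%) fails alone, since 101 are needed. Adding 51/55 unscanned gives 150/165, a pass.
- Ventricular: 84/92 scanned (91.3%) fails alone, since 87 are needed. Adding 44/46 unscanned gives 128/138, a pass.

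In expectation, the pooled rate equals the OPC when the scanned rate is (0.85 − 0.93/3)/(2/3) = 81% atrial, or (0.87 − 0.95/3)/(2/3) = 83% ventricular.

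**The case against.** The strongest reply is that the bracketed condition is leftover wording with no effect. The design has no second group, so everyone in the MRI phase is in the MRI group. The success definition needs a post-scan amplitude, Section 4.2 defines efficacy around the scan, and Section 4.1 lists the scan as part of the MRI visit, so MRI visit data may already imply a scan. Section 4.4.6.2 also mentions a separate Control visit in the data system.

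The leftover explanation is probably right, and these passages point to the intended reading. They do not settle it. They conflict with a criterion that defines a primary analysis set, and 4.4.6.2 uses the same visit names for Controls. The additional analyses do not help: for sensing they are done only if required, and they address missing data.

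Three further points stand and limit the concern.

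- **Retention is inferred from silence.** The protocol does not say that unscanned completers are kept for the OPC analysis. The phrase "including patients who were randomized to the MRI Control Group in previous versions of the investigational plan" can equally describe Controls who re-consent and are scanned.
- **The share is unknown.** A reader might take 29:15 as the allocation ratio and infer that about a third of the 363 are unscanned. The documents do not support this: the figure is the make-up of a 44-patient adverse-event summary, and Controls may cross over.
- **Other endpoints guard the overall claim.** All primary safety and efficacy endpoints must pass, and the capture and MRI safety lists require a scan. A reader might infer that unscanned patients could carry the whole efficacy claim; they could not.

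**Conclusion.** The point holds as a conflict in the definition of a primary analysis set. Section 4.2.3.4 admits, on a literal reading, patients whom the endpoint's own definition and the sister lists exclude. The size cannot be fixed from the documents. It runs from nothing, if no Control completed both visits unscanned, through 2.6% to 3.6% with 15 such patients, to 12% (atrial) and 14% (ventricular) at one third, against a nominal 2.5%.

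These figures assume that scanned patients sit exactly at the OPC, that unscanned patients succeed at the plan's expected rates, and that the exact interval is used. If scanning does not affect sensing, the mixture causes no bias. Dilution could change the overall conclusion only when a scan effect is confined to sensing, leaving capture and safety to pass. The planned sample sizes are correct. The reason to act is that the ambiguity touches two primary endpoints and can be removed by wording alone.

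**What to change.** 1. In the sensing per-protocol list (4.2.3.4, Analysis), replace the conditional scan criterion with: Received the study MRI scan.
2. In the baseline criterion of that list, delete the reference to the pre-waiting period, leaving the pre-MRI amplitude.
3. State for the MRI endpoints that, for a former Control who crosses over, only the visit pair around the actual scan counts. Such a patient may have two pairs, and no section says which is used.

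A descriptive report of the Control-period pairs, as an unscanned reference, is optional. The 44-patient adverse-event summary in 4.2.6 is not a sensing analysis set and need not change for this purpose.

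**Cost.** No new visits or data items. The sensing denominator falls by the number of unscanned Controls, which is unknown, and the planned 165 and 138 must then be met by scanned patients.
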